9. RESEARCH METHOD

Data for the study will be collected in two stages. In stage 1, patients will be visited before surgery (3-4 weeks before for the intervention group, 1 day before for the control group) and informed about the researchers and the study. Patients who agree to participate and meet the inclusion criteria will be included in the study. Patients will be interviewed face-to-face, and they will complete a patient information form prepared by the researchers based on literature, a mini nutritional test, a 6-minute walk test, and the Borg scale. The intervention group will receive prehabilitation, while the control group will receive routine procedures. Postoperatively, patients will complete a patient information form before discharge, and on the 30th day after surgery, a mini nutritional test, an activities of daily living scale, a postoperative recovery index, a 6-minute walk test, and the Borg scale.

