1. SUMMARY

Title of the Study : Investigation of the Effect of Prehabilitation on Patient Outcomes in Frail Patients Planned for Elective Coronary Artery Bypass Graft

Rationale : To see the effect of preoperative routine and improved practices on the patient after surgery.

Purpose : The purpose of the research is, To determine the effect of prehabilitation care on patient outcomes.

Objective : To evaluate the effect of preoperative prehabilitation on patient outcomes and contribute to the literature.

Population : Frail patients scheduled for elective coronary artery bypass grafting at the University of Health Sciences, Istanbul Mehmet Akif Ersoy Thoracic and Cardiovascular Surgery Training and Research Hospital.

Number of Volunteers : The sample calculation of the study was made using Power (G-power) analysis, and the minimum sample size was calculated as 30 patients for both groups, while the Type I error amount was 0.05 and the power of the test was 0.80 ($\alpha=0.05$, $1-\beta=0.80$).

Research Design : The study was planned as a randomized controlled trial.

Procedure : After obtaining institutional approval, the study will continue until the sample size is reached with patients who meet the criteria. Patients identified with the preoperative mini mental test and frailty scale will be administered a patient information form, mini nutritional test, Charlson Comorbidity Index, and Duke activity status index 3-4 weeks before surgery in the intervention group, and 1 day before surgery in the control group. Before postoperative discharge, the appropriate section of the patient information form and the Clavien Dindo classification will be administered and recorded. On the 30th

postoperative day, the mini nutritional test, Duke activity status index, activities of daily living scale, and postoperative recovery index will be administered and recorded.

Research Duration : After obtaining institutional permission, the study will continue until the sample size is reached on patients who meet the criteria.

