8. POPULATION TO BE STUDIED

How was the sample size decided: It was decided by G-power analysis.

Number of volunteers planned to be included: 30+30

Volunteer Age Range: 60+

- Agreeing to participate in the research,
- Undergoing elective open coronary artery bypass grafting
- Being 60 years old or older,
- Being in the frail patient status as a result of the FRIED Frailty Scale,
- Being able to communicate in Turkish.

Exclusion Criteria: Patients whose surgery has been postponed and those whose mini mental test result is 23 or below will not be included.

Gender: Male and female

Are there any vulnerable groups/individuals (children, disabled people, unconscious individuals) planned to be included?

Yes No

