11. RESEARCH DESIGN / METHOD

The study was planned as a randomized controlled trial.

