12. PROCEDURE TO FOLLOW

The study was planned as a randomized controlled trial to be conducted at the cardiovascular surgery clinic of the Istanbul Mehmet Akif Ersoy Thoracic and Cardiovascular Surgery Training and Research Hospital. Patients meeting the sample selection criteria will be included in two groups. Data will be collected using a patient information form, mini nutritional test, Borg scale, activities of daily living scale, and postoperative recovery index. A 6-minute walk test will be administered and recorded. All data will be collected by the researchers.

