13. EVALUATION AND PARAMETERS TO BE RECORDED

Patients will be interviewed face-to-face and a "Patient Information Form," prepared by the researchers based on literature, will be completed. A mini mental test and frailty scale will be used to select patients. A preoperative mini nutritional test, comorbidity scale, 6-minute walk test, and Borg scale will be used for both groups. A patient information form and complication classification will be completed before discharge. On the 30th postoperative day, a mini nutritional test, activities of daily living scale, postoperative recovery index, 6-minute walk test, and Borg scale will be used.

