15. STATISTICS

The data obtained in the study will be analyzed using SPSS 25.0. Descriptive statistical methods such as number, percentage, mean, and standard deviation will be used in the data analysis. Based on the results, the data will be analyzed using relevant tests (t-test, chi-square, Man-Whitney U, Fisher's exact, and regression analysis).

H0: Prehabilitation does not affect patient outcomes in fragile cases undergoing elective coronary artery bypass grafting.

H1: Prehabilitation affects patient outcomes in fragile cases undergoing elective coronary artery bypass grafting.

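### Information, agreement, inclusion and baseline are scheduled by arm, so allocation comes before enrolment and randomisation does not protect the groups that are compared

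*Protocol*

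**What the plan says.** Section 11 states: "The study was planned as a randomized controlled trial". Sections 1 and 12 say the same.

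Section 9 sets the first contact. Patients are visited before surgery "3-4 weeks before for the intervention group, 1 day before for the control group) and informed about the researchers and the study". The next sentence reads: "Patients who agree to participate and meet the inclusion criteria will be included in the study". The preoperative nutrition test, 6-minute walk and Borg scale follow at that stage.

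Section 1 dates the preoperative forms, including the nutrition test and the Duke index, "3-4 weeks before surgery in the intervention group, and 1 day before surgery in the control group".

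Section 12 adds: "All data will be collected by the researchers". Section 13 gives no dates: "A preoperative mini nutritional test, comorbidity scale, 6-minute walk test, and Borg scale will be used for both groups". Section 17 puts information and consent at a visit before surgery and ahead of data collection, again without a date. Section 8 sets the exclusions: "Patients whose surgery has been postponed and those whose mini mental test result is 23 or below will not be included".

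**The concern.** Randomisation makes groups comparable only for the people who were randomised. If agreement and eligibility are settled after the arm is set, and at different times in the two arms, the enrolled groups have passed through different gates. A control must have reached the day before surgery, while an intervention patient is taken on weeks earlier. Patients who drop out of view between allocation and the control visit are never enrolled or counted, so an intention-to-treat analysis of enrolled patients cannot bring them back. Every outcome is exposed.

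There is a second, narrower consequence. Baseline is measured at unlike distances from surgery, so a change from baseline, or an adjustment for it, does not compare like with like.

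**Working it through.** **Order of events.** Section 9 gives the sequence: a visit timed by arm, then information, then agreement and eligibility, then inclusion and baseline measures. For the visit to be timed by arm, the arm must already exist and be known at least to the researchers who arrange it. By Section 12 the researchers also collect all the data. Whether patients are told their arm is not stated, and nothing here depends on it. Random selection of names from the surgical list would not change this: allocation would still precede consent.

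**Timing, from the protocol.** Entry is 21-28 days before surgery (intervention) against 1 day (control). Baseline to day 30 spans 21 + 30 = 51 to 28 + 30 = 58 days, against 1 + 30 = 31 days. The ratios are 51/31 = 1.65 and 58/31 = 1.87.

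**Scale of the trial.** The protocol gives 30 per group, alpha 0.05 and power 0.80, but no effect size, SD or sidedness, so its sample size cannot be reproduced. Solving backwards, two-sided, the normal approximation gives (1.960 + 0.842) × √(2/30) = 0.72 SD; the t-test gives 0.736 SD.

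**Illustration 1: selection (any outcome).** Suppose a fraction f of one arm is selectively not entered and differs from the rest by d SD. The false difference is f × d. Rejection rates are for a two-sided 5% t-test, 30 per arm, no treatment effect:

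| f | d (SD) | False difference (SD) | Rejection |
|---|---|---|---|
| 0.1 | 0.3 | 0.03 | 5.15% |
| 0.2 | 0.5 | 0.10 | 6.7% |
| 0.3 | 0.5 | 0.15 | 8.8% |

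A different model enrols only the top 60-90% of one arm on a factor correlated 0.3-0.5 with outcome, and the other arm in full. It gives shifts of 0.06-0.32 SD and rejection of 5.6-23%. The inputs to both models are assumptions.

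**Illustration 2: postponement, only if the Section 8 bar is also applied after entry.** Assume a weekly postponement rate w of 2-5%. The share excluded is 1 − (1 − w)^(days/7).
- w = 0.02: 5.9% at 21 days, 7.8% at 28 days, 0.3% at 1 day.
- w = 0.05: 14.3%, 18.5% and 0.7%.
- Out of 30: about 1.8-5.6 intervention patients against 0.1-0.2 controls.

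**Illustration 3: baseline timing, only if a change score or baseline adjustment is used.** Assume the measure drifts by 0.1, 0.2 or 0.3 SD over the 3-4 weeks, with no treatment effect (20,000 simulated trials, 30 per arm). Each cell gives the results for the three drifts in order.

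| Baseline to day-30 correlation (intervention / control) | Change score, rejection | Adjusted, bias (SD) | Adjusted, rejection |
|---|---|---|---|
| 0.6 / 0.6 | 7.3 / 13.6 / 24.8% | 0.06 / 0.12 / 0.18 | 5.8 / 8.9 / 13.1% |
| 0.5 / 0.7 | 6.9 / 13.3 / 24.7% | 0.06 / 0.12 / 0.18 | 5.7 / 8.6 / 13.5% |
| 0.5 / 0.6 | 6.9 / 12.7 / 22.7% | 0.05 / 0.11 / 0.16 | 5.9 / 7.9 / 11.3% |

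The change-score comparison is off by the drift itself. A comparison of day-30 values alone has no bias from drift and rejects 4.8-5.2% of the time. Reversing the drift reverses the sign.

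**The case against.** **Selection may precede grouping.** Section 12 can be read as placing eligible patients into two groups, and Sections 1 and 13 mention the cognitive and frailty screens without an arm-specific date. A common screen before the arms separate is therefore possible. This stands for those two criteria only. It does not move information or agreement ahead of the visit that Section 9 times by arm. Section 17 gives no date and does not supply an earlier common consent step. The point does not rely on any missing description of the randomisation procedure.

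**Postponement may act the other way.** Section 8 reads most naturally as an entry rule. On that reading a patient postponed before the day-before visit is kept out of the control arm, while an intervention patient already enrolled is not, so the burden falls mainly on controls. That is fair. It is one reason the direction of bias is left open and illustration 2 is conditional.

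**Baseline timing may never matter.** Section 15 says "Based on the results, the data will be analyzed using relevant tests (t-test, chi-square, Man-Whitney U" and goes on to include regression, but names neither a change score nor baseline adjustment. The analysis model may be fixed elsewhere. This stands, and illustration 3 is secondary.

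**The illustrative sizes are modest and depend on the inputs.** True. They show scale and do not establish the defect.

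**Conclusion.** The concern holds. Followed as written, Sections 1 and 9 put allocation before information, agreement, inclusion and baseline, which is incompatible with the protection implied by calling the trial randomised. It must be fixed before enrolment, because no analysis can recover the patients who were never entered.

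The part that rests on the protocol alone is the order of events and the unequal timing: entry at 21-28 days against 1 day, and 51-58 days against 31 from baseline to day 30. The size and direction of bias cannot be determined from the protocol. Under the first selection assumption it is 0.03-0.15 SD either way, set against a trial that detects about 0.74 SD (two-sided t-test, 80% power). The postponement and baseline-timing figures apply only under the readings stated with them and do not carry the conclusion.

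**What to change.** Rewrite Sections 1, 9 and 17 so that patients in both arms are screened, informed, consented and measured at baseline at the same visit 3-4 weeks before surgery. Randomise, with concealed allocation, only after baseline is recorded. If a day-before measurement is wanted, take it in both arms as a separate time point, not as baseline. State in Section 8 that the postponement exclusion applies only before randomisation, keep patients postponed later in their allocated arm, and report by arm those who never reach surgery.

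The cost is an amendment and earlier contact with controls. Patients who never reach surgery have no discharge or day-30 outcome. The present design already carries that loss in the intervention arm, so the added loss is in controls. Assuming 5-10% per arm, 30 × 0.95 = 28.5 to 30 × 0.90 = 27 per arm are evaluable. Power at 0.736 SD falls from 80% to about 76-78%, and the detectable effect rises to about 0.76-0.78 SD.

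Keeping 30 evaluable would take 30/0.95 = 31.6, so 32, to 30/0.90 = 33.3, so 34, randomised per arm. The repair does not depend on that increase. If the Section 1 rule of recruiting until the target is met refers to evaluable patients, the cost is longer recruitment rather than lost power.

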10. RESEARCH PRODUCT / TREATMENT

No products or drugs will be used in the study.

11. RESEARCH DESIGN / METHOD

The study was planned as a randomized controlled trial.

12. PROCEDURE TO FOLLOW

The study was planned as a randomized controlled trial to be conducted at the cardiovascular surgery clinic of the Istanbul Mehmet Akif Ersoy Thoracic and Cardiovascular Surgery Training and Research Hospital. Patients meeting the sample selection criteria will be included in two groups. Data will be collected using a patient information form, mini nutritional test, Borg scale, activities of daily living scale, and postoperative recovery index. A 6-minute walk test will be administered and recorded. All data will be collected by the researchers.

13. EVALUATION AND PARAMETERS TO BE RECORDED

Patients will be interviewed face-to-face and a "Patient Information Form," prepared by the researchers based on literature, will be completed. A mini mental test and frailty scale will be used to select patients. A preoperative mini nutritional test, comorbidity scale, 6-minute walk test, and Borg scale will be used for both groups. A patient information form and complication classification will be completed before discharge. On the 30th postoperative day, a mini nutritional test, activities of daily living scale, postoperative recovery index, 6-minute walk test, and Borg scale will be used.

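### No visible schedule records events between first visit and operation, and with unequal entry times they can drop out of the intervention arm only

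*Protocol*

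**What the plan says.** **Recording points.** Section 9 states "Data for the study will be collected in two stages": a preoperative visit, then postoperative collection. The Summary and Section 13 give the same time points: preoperative scales, then discharge, then day 30. For discharge, Section 13 says "A patient information form and complication classification will be completed before discharge"; the Summary names the classification as Clavien Dindo and places it before postoperative discharge. Day 30 holds nutritional, functional and recovery scales. Section 12 lists instruments only.

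**Entry.** The Summary and Section 9 place the first visit 3-4 weeks before surgery in the intervention arm and 1 day before surgery in the control arm.

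**Population.** The Summary has "Frail patients scheduled for elective coronary artery bypass grafting". Section 8 has "Undergoing elective open coronary artery bypass grafting" and does not include patients whose surgery has been postponed. Both hypotheses in Section 15 refer to cases *undergoing* elective bypass grafting.

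**Size.** Section 8: "Number of volunteers planned to be included: 30+30".

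**The concern.** Prehabilitation is given before the operation, so the weeks between first visit and operation are when the arms are treated differently. The aim is its effect on patient outcomes. Yet no listed parameter would capture a death, an infarction, an unplanned admission, a fall, a move to urgent surgery or a cancelled operation in that time.

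The population wording makes this worse. For an intervention patient, whether elective surgery takes place is known only after the 3-4 weeks. If *undergoing* is taken literally, a patient who never reaches elective surgery fails an inclusion criterion after having been enrolled. A control enrolled the day before surgery has almost no time in which this can happen.

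Two things are at stake. Harm during the intervention period may go unreported, and the intervention arm that reaches the postoperative comparison may be a selected one. Events that were never collected cannot be recovered by an analysis plan.

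**Working it through.** **1. Inputs.** From the documents: 30 patients per arm (Section 8), first visit 21-28 days or 1 day before surgery (Summary, Section 9), last assessment on day 30 (Summary, Sections 9 and 13). The first visit is taken as entry, because the visible text does not say when allocation takes place. The documents give no preoperative event rate, so every rate below is an assumption.

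**2. The plan's own figure.** The Summary gives "the Type I error amount was 0.05 and the power of the test was 0.80" and says "the minimum sample size was calculated as 30 patients for both groups"; Section 8 makes this 30 per arm. No effect size, variance or event rate is stated, so the number cannot be reproduced forward. Solved backward (two-sided), d = (1.960 + 0.842) × √(2/30) = 0.72, or 0.74 (0.736) with the t distribution. It is used only in step 5.

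**3. Time not covered.** For an intervention patient, 21/(21 + 30) = 41% to 28/(28 + 30) = 48% of the time from first visit to day 30 lies before the operation. For a control it is 1/(1 + 30) = 3%. These are shares of calendar time, not measures of harm.

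**4. Patients affected.** Expected number = 30p; chance of at least one = 1 − (1 − p)^30.

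| Assumed risk p | Expected of 30 | Chance of at least one |
|---|---|---|
| 3% | 0.9 | 60% |
| 5% | 1.5 | 79% |
| 10% | 3.0 | 96% |

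**5. Power or bias?** At d = 0.736, losing 1 to 5 of the 30 intervention patients lowers power from 0.80 to between 0.79 and 0.76. Loss of power is not the problem.

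**6. Illustration of the bias (invented counts).** Let 9 of 30 enrolled patients in each arm have a bad outcome, so there is no difference. Let k of the 9 in the intervention arm occur before surgery and be dropped. The apparent difference is (9 − k)/(30 − k) − 9/30.

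| k | Operated intervention patients | Control | Apparent difference |
|---|---|---|---|
| 1 | 8/29 = 27.6% | 30% | −2.4 points |
| 3 | 6/27 = 22.2% | 30% | −7.8 points |
| 5 | 4/25 = 16.0% | 30% | −14.0 points |

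This takes the controls as enrolled, at 30%. Suppose instead that the wait had already thinned the control pool in the same way before enrolment (3 of every 30, all with bad outcomes). Its rate would then also be 6/27 = 22.2%, and the postoperative difference would be zero. What would be lost in that case is the preoperative events themselves. The table shows how the tilt can arise; it does not estimate its size.

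**The case against.** **The gap is an absence, and the copy is incomplete.** The part between Sections 13 and 15 was not available, and the content of the patient information form is not shown. That form is completed before surgery and again before discharge, so it could hold interval events for patients who reach the operation. This stands. A reader might infer that preoperative harm can never enter the comparison; the documents do not support that. They support only that no visible schedule lists it.

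***Undergoing* may just mean scheduled.** Section 9 applies the inclusion criteria at the preoperative visit, when surgery can only be planned. No text says that an enrolled patient who dies or goes to urgent surgery is removed. This is fair: exclusion after enrolment is one possible reading, not a stated rule. But the Summary and Section 8 use different words, no visible text says such patients are kept, and the postponement criterion in Section 8 points the other way.

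**The direction of bias depends on entry times.** This also stands. A reader might infer that the tilt towards prehabilitation would persist if both arms entered together. It would not follow: both arms would then lose patients before surgery, and if prehabilitation reduced such losses its arm would keep frailer patients. Only the recording gap would persist. Even under the present design the tilt is a tendency, as the last case in the working shows.

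**A by-arm count is unfair as things stand.** Recording events from first visit to operation would set 21-28 days against about 1 day and load events onto prehabilitation. This is correct, and the remedy must include a common starting point.

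**Conclusion.** The point holds in a limited form. No visible schedule records events between first visit and operation, and the population is described in two ways that part company for exactly the patients who have such events. Because intervention patients enter 3-4 weeks before surgery and controls 1 day before, these patients can drop out of the intervention arm only. That tends to favour prehabilitation in the postoperative comparison.

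The size is unknown. At assumed risks of 3-10%, 0.9-3 of 30 intervention patients would be affected; the apparent differences in the illustration rest on invented counts. The 41-48% share of time should not be read as the size of the bias. With equal entry times the recording gap would remain, without a known direction of bias. All of this is subject to the missing part of the protocol and the unseen form. It is nevertheless a matter for the protocol, which fixes what is collected and who is eligible.

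**What to change.** 1. **Record the period.** In Sections 9 and 13, add one item taken from hospital records for both arms: death, myocardial infarction, unplanned admission, fall, change to urgent surgery, operation postponed or not done. Report it by arm.
2. **Use a common start.** The item should run from a common allocation point, 3-4 weeks before surgery in both arms, to the operation. The control-arm timing in the Summary and Section 9 must be changed to match. Without this the by-arm comparison is not fair.
3. **Align the population.** In Sections 8 and 15, replace *undergoing* with *scheduled for*, as in the Summary. Apply the eligibility criteria, including the one on postponement, only at allocation; otherwise that criterion would contradict item 4.
4. **Keep everyone.** State that every allocated patient is kept and reported in the allocated arm, with non-operation shown as an outcome.

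**Cost.** A protocol amendment, one extra form item from existing records, and earlier contact with control patients. A few patients will have no postoperative scores and must be shown as such. If the missing part of the protocol or the patient information form already records these events, item 1 reduces to a cross-reference; items 2 to 4 still apply.
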